2. STUDY OBJECTIVES

2.1 Primary Objectives

Main objectives of this study are:

- to investigate the short term profile of CHF 5633 vs. porcine surfactant (Poractant Alfa, Curosurf®) in terms of reduced oxygen requirement and ventilatory support
- to evaluate the mid-term profile in terms of incidence of BPD and mortality/BPD rate at 36-week post menstrual age (PMA), mortality rate at 28 days PNA and at 36 weeks PMA, RDS-associated mortality through 14 days of age and other major co-morbidities of prematurity.

2.2 Secondary Objectives

- To evaluate the need for re-dosing in the two treatment groups;
- to evaluate the inflammatory status through the measurements of specific biomarkers of inflammation in tracheal aspirates (in a subgroup of babies who require endotracheal intubation for mechanical ventilation, when feasible);
- to assess immunogenicity through the measurement of antibodies to SP-B analogue (CHF 5736.03) and SP-C analogue (CHF 4902.03) contained in CHF 5633
- to perform the evaluation of invasive measurements of ventilator support (in a subgroup of babies when feasible);
- to evaluate the safety profile in the two treatment groups in terms of adverse events (AEs) and adverse drug reactions (ADRs), vital signs, hematology and biochemistry values.

3. STUDY DESIGN

This is a multicenter, double blind, randomized, single dose, active-controlled study. Efficacy and safety assessments will be performed in the 24 hours following study treatment administration (at minutes 30, at hours 1, 3, 6, 12, 18 and 24), in the next 6 days (at days 2, 3, 5 and 7) and in the follow-up periods [(at days 28±2 postnatal age (PNA), discharge home and at 36 weeks postmenstrual age (PMA)]. Moreover, a further clinical assessment will be performed at 24 months (±3 months) corrected age to check the neurological and general health status related to the condition of prematurity (Table 1).

TABLE 1: TIMETABLE

| TREATMENT A CHF5633 (synthetic surfactant) 200 mg/kg (re-dosing if needed with CHF5633 100mg/kg) | | | | | | | | | | | | | | |
|---|--|--|--|--|--|--|--|--|--|--|--|--|--|--|
|---|--|--|--|--|--|--|--|--|--|--|--|--|--|--|

| TREATMENT B Poractant Alfa (porcine surfactant) 200 mg/kg (re-dosing if needed with Poractant Alfa 100mg/kg) | | | | | | | | | | | | | | |
|---|--|--|--|--|--|--|--|--|--|--|--|--|--|--|
|---|--|--|--|--|--|--|--|--|--|--|--|--|--|--|

| Time | Within 24 hours | 0 | 30' | 1h | 3h | 6h | 12h | 18h | 24h | 2 days | 3 days | 5 days | 7 days | 28 days PNA | Discharge home | 36 wks PMA | 24 - month clinical assess. |
|-------|-----------------|---|-----|----|----|----|-----|-----|-----|--------|--------|--------|--------|-------------|----------------|------------|-----------------------------|
| Phase | 1 | | | | | | | | | 3 | 4 | 5 | 6 | 7 | 8 | 9 | 10 |

 Randomisation
 and Test treatment
 administration

End of the trial

The end of the trial will correspond to the date of discharge home of the last baby from the approved investigational sites (recruiting sites) or from another hospital where the treated baby could have been transferred from the original recruiting site for continuation of clinical care.

In case the last baby is discharged home prior to 36-week PMA, the end of the trial will correspond to a clinical assessment at 36-week PMA (on-site visit or phone call).

The approved investigational site is responsible for the proper follow-up, data collection and documentation of the primary and secondary outcomes until the baby is discharged home. The investigator of the recruiting site will have to keep contacts and provide the continuing care site with written instruction about management of the above as well as for the reporting of serious AE, if any.

4. SUBJECT SELECTION CRITERIA

4.1 Subject Recruitment

The study population consists of premature neonates with RDS. Up to one hundred and twenty-six (126) patients of either sex with clinical finding of RDS (63 in each treatment arm) are expected to be randomized in the study. In this trial the eligible neonates will be drawn from those born in the collaborating centers (inborn neonates), who meet all the inclusion and none of the exclusion criteria. No limitation by ethnic origin, gender or social status will be used. RDS is defined in the study population by the presence of respiratory symptoms and signs in the first 24 hours of life, associated to the need for increased inspired oxygen requirements.

4.2 Inclusion Criteria

Subjects must meet all the following inclusion criteria to be eligible for enrolment into the study:

1. Written informed consent obtained by parents/legal representative (according to local regulation) prior to any study-related procedures
2. Inborn preterm neonates of either sex with a gestational age of 24^{+0} weeks up to 29^{+6} weeks
3. Clinical course consistent with RDS
4. Requirement of endotracheal surfactant administration within 24 hours from birth
5. Fraction of inspired oxygen (FiO_2) ≥ 0.30 for babies 24^{+0} to 26^{+6} weeks and $\text{FiO}_2 \geq 0.35$ for babies 27^{+0} to 29^{+6} weeks to maintain SpO_2 between 88–95%.

4.3 Exclusion Criteria

The presence of any of the following will exclude a subject from study enrollment:

1. Use of surfactant prior to study entry and need for intratracheal administration of any other treatment (e.g. nitric oxide)
2. Known genetic or chromosomal disorders, major congenital anomalies (cardiac malformations, myelomeningocele etc)
3. Mothers with prolonged rupture of the membranes (>21 days duration)
4. Strong suspicion of congenital pneumonia/infection, sepsis
5. Presence of air leaks if identified and known prior to study entry
6. Evidence of severe birth asphyxia
7. Neonatal seizures prior to study entry
8. Any condition that, in the opinion of the Investigator, would place the neonate at undue risk
9. Participation in another clinical trial of any placebo, drug or biological substance conducted under the provisions of a protocol.

4.4 Subject Withdrawals

Parents/legal representative have the right to withdraw the subject from the study at any time for any reason.

The Investigator has also the right to withdraw the subjects from the study in the event of:

- An adverse event which is considered intolerable by the Investigator prior to or after surfactant administration
- An abnormal laboratory test result that the Investigator considers clinically significant and warranting the withdrawal of the subject prior to surfactant administration.
- An intercurrent clinical condition/disorder/anomaly that necessitates pharmacological treatment with a drug which interacts in any way with the test treatment prior to surfactant administration
- The development of any exclusion criterion prior to surfactant administration.

The Investigator is responsible for the optimal individual treatment for the subject. The Investigator must fill in the “Study Termination” page in the electronic case report form (eCRF) explaining the main reason for withdrawal.

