10.5 Action taken with study drug due to the AE

Since patients will receive a single dose of study drug, “action taken with study drug” will be not applicable.

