#### ***RDS-Mortality***

The RDS-associated Mortality incidence through 14 days of age will be surveyed in the corresponding treatment group. Patients with reasons for discontinuation='RDS RELATED DEATH" and died within 14 days of age will be considered in the counts.

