### ***Mortality/BPD incidence***

The mortality/BPD incidence at 36-week PMA will be defined as:

Incidence of neonates dead within 36-week PMA or alive at 36-week PMA with a diagnosis of BPD.

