### 6.3.4 Missing Data

Generally there will be no imputation of missing data. Hence critical missing data, if any, will be discussed during the BDRM before database lock. Decisions will be fully documented in the BDRM Report.

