## Statistical Analysis Plan

Only GA factor is included since not possible to use the combination of two factors (i.e. too few neonates by site). Please refer to DR report \*/

The incidence of BPD at 36-week PMA will be compared by treatment as for Mortality/BPD incidence. Cases not assessed at 36-week PMA visit won't be imputed. Missing cases won't be included in test statistics computation.

The mortality incidence at 36-week PMA and at Day 28 will be compared by treatment as for Mortality/BPD rate.

RDS-associated mortality incidence through 14 days of age will be compared by treatment as for Mortality/BPD rate.

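### Investigator withdrawal from the study after dosing may lose BPD and vital status in an outcome-related way, because nothing expressly requires 36-week outcomes to be collected afterwards

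*Protocol*

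**What the plan says.** **Withdrawal.** Protocol 4.4 introduces the investigator's grounds with "The Investigator has also the right to withdraw the subjects from the study in the event of", and the first is "An adverse event which is considered intolerable by the Investigator prior to or after surfactant administration". The other three grounds apply only before surfactant is given, so this is the only one open after the dose. The text does not define what counts as intolerable. The main reason is then recorded on the study termination page.

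**Treatment.** Protocol 10.5 treats action taken with study drug as not applicable: "Since patients will receive a single dose of study drug". Protocol 7.1 allows up to two repeat doses.

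**Missing outcomes.** SAP 6.3.4 says "Generally there will be no imputation of missing data" and refers critical missing data to the blind data review. For BPD, SAP 6.3.12.1.7 is explicit: "Cases not assessed at 36-week PMA visit won't be imputed. Missing cases won't be included in test statistics computation".

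**Endpoints.** SAP 6.1.4.8 defines the composite as "Incidence of neonates dead within 36-week PMA or alive at 36-week PMA with a diagnosis of BPD". For RDS mortality it counts "Patients with reasons for discontinuation='RDS RELATED DEATH" with death by 14 days of age.

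**The concern.** An adverse event after the dose may bear on further study treatment, but it gives no reason to stop recording outcomes. Section 4.4 does not separate the two: what it permits is withdrawal from the study. A baby withdrawn for a severe event probably has a higher risk of BPD or death than one who stays. If 36-week status is then unknown, it is missing for a reason related to the outcome.

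BPD, mortality/BPD, mortality and RDS mortality all belong to the main objectives (Protocol 2.1, SAP 1.1). With at most 63 babies per arm, a few lost outcomes can shift a risk ratio. If one product caused more such events, its arm could lose more outcomes and look better than it is.

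**Working it through.** **Step 1: is the outcome secured elsewhere?**

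- Protocol 10.8: adverse event recording stops when participation ends. SAE follow-up may go on after the baby leaves the study, for pharmacovigilance. It has no time limit for related SAEs and is decided case by case for unrelated ones.
- Protocol 10.9: SAE reporting also stops when participation ends, except for SAEs that the investigator considers related.
- Protocol 7.1.7 and 7.1.9: recall for the day-28 and 36-week assessments covers babies discharged or transferred. Withdrawn babies are not mentioned.
- Protocol 3 (end of the trial): the site is responsible for outcome data until discharge home. The text does not say whether this survives withdrawal.
- Protocol 12.2 and SAP 6.2.2: a dosed baby with one post-baseline efficacy value is in the ITT population, so a withdrawn baby can be in ITT with no 36-week outcome.

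None of these expressly requires BPD or vital status at 36 weeks PMA after withdrawal.

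**Step 2: how does the SAP treat such a baby?**

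- BPD: left out of the test.
- Mortality and mortality/BPD: no rule for unknown status.
- RDS mortality: a baby whose recorded reason is an adverse event, and who dies of RDS by day 14, does not meet the counting rule even if the death is known.
- No sensitivity analysis for missing outcomes is given.

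**Step 3: possible size.** The documents give 63 per arm and no event rate, withdrawal rate or power calculation, so there is no planned figure to reproduce. Assume the same true risk p in both arms (RR 1.00) and k babies withdrawn from one arm only, all of whom would have had the event.

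- Left out: risk = (63p − k)/(63 − k).
- Kept in the denominator as non-events: risk = (63p − k)/63.
- RR = that risk divided by p.

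| p (assumed) | k | Left out: risk | RR | Kept as non-event: risk | RR |
|---|---|---|---|---|---|
| 0.50 | 1 | 30.5/62 = 0.492 | 0.98 | 30.5/63 = 0.484 | 0.97 |
| 0.50 | 3 | 28.5/60 = 0.475 | 0.95 | 28.5/63 = 0.452 | 0.90 |
| 0.50 | 5 | 26.5/58 = 0.457 | 0.91 | 26.5/63 = 0.421 | 0.84 |
| 0.30 | 1 | 17.9/62 = 0.289 | 0.96 | 17.9/63 = 0.284 | 0.95 |
| 0.30 | 3 | 15.9/60 = 0.265 | 0.88 | 15.9/63 = 0.252 | 0.84 |
| 0.30 | 5 | 13.9/58 = 0.240 | 0.80 | 13.9/63 = 0.221 | 0.74 |
| 0.10 | 1 | 5.3/62 = 0.085 | 0.85 | 5.3/63 = 0.084 | 0.84 |
| 0.10 | 3 | 3.3/60 = 0.055 | 0.55 | 3.3/63 = 0.052 | 0.52 |
| 0.10 | 5 | 1.3/58 = 0.022 | 0.22 | 1.3/63 = 0.021 | 0.21 |

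At p = 0.10 only 6.3 events are expected per arm, so k = 5 is an extreme case.

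A real difference can also be hidden. With true risks of 0.15 v 0.10 (RR 1.50), three such withdrawals from the worse arm give (9.45 − 3)/60 = 0.1075, so the RR falls to 1.08.

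If both arms lose the same k at equal true risk, the RR stays at 1.00 but both rates are understated (p = 0.50, k = 3: 0.475 in each arm).

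**Step 4: what missing status leaves open.** With m unknown per arm, the best-case and worst-case risk differences lie 2m/63 apart: 0.03, 0.10 and 0.16 for m = 1, 3 and 5.

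**The case against.** A reader might infer that section 4.4 takes the sickest babies out of follow-up. The documents do not support that. The clause gives a discretionary right, no withdrawal rate is stated, and deaths during participation are counted.

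A reader might also infer that mortality is lost wholesale. Many events severe enough for withdrawal would be serious. Continued SAE follow-up, the fatal outcome category (Protocol 10.7) and the death narrative (10.11) would bring some later deaths to light. Non-serious events and later unrelated deaths are not reliably covered, and nothing routes deaths learned of this way into the efficacy endpoints.

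Nor is the whole analysis complete-case. Explicit exclusion stands only in the BPD paragraph, and the first-24-hour mixed model uses all available repeated values. No bias in the ventilation or oxygen durations has been shown.

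With equal true risks, a spurious treatment difference needs withdrawals that differ by arm or by the risk of those withdrawn. Blinding makes this less likely, but a true safety difference could produce it. At high event rates the shift can be small against sampling error. If the true rate is 34/63 in both arms and 5 v 1 future events are withdrawn, the result is 29/58 (50.0%) v 33/62 (53.2%). That is 3.2 points against a standard error of √(0.500 × 0.500/58 + 0.532 × 0.468/62) = 9.1 points, or about one-third of a standard error. The study is also exploratory, with no power claim.

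Finally, the site's general duty to document outcomes until discharge could be read to include withdrawn babies. That makes the gap one of unclear wording rather than a stated end to collection. These points limit the size and certainty of the problem; they do not close the gap.

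**Conclusion.** The concern holds as a gap in outcome collection and endpoint rules. Section 4.4 allows a severity-related exit from the study after dosing, and nothing expressly secures 36-week BPD or vital status afterwards. The SAP then excludes unassessed babies from the BPD test, is silent on unknown status for mortality and the composite, and ties RDS mortality to the discontinuation reason. Outcome-related loss is possible; it is not shown to occur.

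No single figure for the bias can be given. It is modest for common outcomes and can be large for rare ones such as mortality, where one to three lost events give an RR of 0.85 to 0.55 at an assumed 10% risk if those babies are left out. These figures rest on assumed event rates, withdrawals in one arm only, and every withdrawn baby having the event. What is affected is the interpretation of the mid-term main-objective outcomes, not a stated sample size.

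**What to change.** Leave the investigator's treatment and withdrawal decisions unchanged, and make these changes to data collection and analysis:

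1. In Protocol 4.4, state that withdrawal does not end outcome collection unless the parents withdraw consent to it.
2. Collect vital status at day 28 and at 36 weeks PMA, and BPD status at 36 weeks PMA, for every dosed baby. Name withdrawn babies in the recall text of 7.1.7 and 7.1.9.
3. In SAP 6.1.4.8, derive RDS mortality from cause and date of death, not from the discontinuation reason.
4. In SAP 6.3.12.1.7, state how unknown status enters each binary endpoint, and add a best/worst-case sensitivity analysis for babies with unknown status.

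The cost is a protocol and SAP wording change, a little extra site follow-up at assessments already planned, and some analysis work. If status were known for every dosed baby, the distortion in the table and the width in step 4 would both be zero.

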5. CONCOMITANT MEDICATIONS

Subjects may be treated with other medications as needed in the critical care situation. The treating physician will manage neonates as he/she deems to be in their best interests. Concomitant medications will be recorded in the CRF.

5.1 Permitted concomitant Medications

Any concomitant medication required for the normal care of preterm neonates will be permitted during the study.

5.2 Non-permitted previous and concomitant Medications

1. Surfactant treatment prior to study entry
2. Intratracheal administration of any other treatment (e.g. nitric oxide) prior to study entry
3. Other investigational drugs.

6. TREATMENT(S)

6.1 Appearance and Content

The drug product CHF 5633 is a sterile suspension, with a pH of 6.0 compatible with the physiologic one in the lungs' and designed specifically for endotracheopulmonary instillation. The suspension contains a combination of two phospholipids and two peptides, in a sterile saline solution at the final concentration of 80 mg/ml. The drug product is filled in sealed 3.0 ml glass vials under nitrogen atmosphere. The composition is reported in the table below.

Table 2.4/5: Drug Product composition

| Ingredients | Quantity per mL (mg) | Function |
|---|-------------------------|-------------------------------|
| CHF 4902.03 (SP-C analogue) | 1.2 | Surfactant's co-adjvant agent |
| CHF 5736.03 (SP-B analogue) | 0.16 | Surfactant's co-adjvant agent |
| CHF 5300.00 (DPPC) | 39.32 | Surfactant |
| CHF 5301.02 (POPG, sodium salt) | 39.32 | Surfactant |
| 0.9% sodium chloride sterile solution for injection | q.s. to 1.0 mL | Suspending agent |
| 1% sterile acetic acid to pH | q.s to pH | pH adjustment agent |
| 1.4% sodium bicarbonate sterile solution qs to pH | q.s to pH | pH adjustment agent |

Sterile nitrogen flow is used to flush bottle's head space.

Poractant Alfa (Curosurf[®]) is a standard natural surfactant treatment prepared from porcine lungs for intratracheal administration and containing almost exclusively polar lipids, in particular phosphatidylcholine (about 70% of the total phospholipid content), and about 1% of specific low molecular weight hydrophobic proteins SP-B and SP-C, with a total concentration of 80 mg/ml. The drug product is filled in sealed 3.0 ml glass vials.

Chiesi Farmaceutici S.p.A. will supply the study medication and also provide the Pharmacist/Investigator with appropriate certificates of analytical conformity.

6.2 Dosage and Administration

6.2.1 Selection of doses in the study

Surfactant doses used in the study follow the recommendations approved in the USA SmPC for the administration of Poractant Alfa (Curosurf[®]), determined as 200 mg/kg for the first dose and 100 mg/kg for additional doses. For this reason, CHF 5633 will be initially administered at the dosage of 200 mg/kg (total drug substance components).

Pharmacodynamic studies, both in vitro and in vivo in premature newborn rabbits⁽¹⁶⁾, showed that 200 mg/kg of CHF 5633 has a profile comparable to that of approved naturally derived surfactants (Survanta[®] and Poractant Alfa, Curosurf[®]).

In the FIH trial⁽¹⁷⁾ a lower dose of 100 mg/kg was included for safety reasons and showed to be safe and effective. The same positive profile was demonstrated for the upper dose of 200 mg/kg.

Extreme preterm neonates' lungs present very immature features, such as simplified saccular airways, no true alveoli and wide interstitial spaces, making them very susceptible to lung injury⁽¹⁸⁾. Given the vulnerability of this population, the higher dose of 200 mg/kg has been chosen to achieve a clear efficacy signal and the possible greatest beneficial effect.

6.2.2 Dosage

CHF 5633 2.5 ml/kg (200 mg/kg) sterile suspension in one single intratracheal administration within 24 hours from birth.

CHF 5633 1.25 ml/kg (100 mg/kg) will be used for further re-dosing when needed (up to two repeat doses).

Poractant Alfa (Curosurf[®]) 2.5 ml/kg (200 mg/kg) sterile suspension in one single intratracheal administration within 24 hours from birth. .

Poractant Alfa 1.25 ml/kg (100 mg/kg) will be used for further re-dosing when needed (up to two repeat doses).

6.2.3 Administration

Before the administration of CHF 5633 or Poractant Alfa, the condition of the neonate should be stabilized, correcting any acidosis, hypotension, anaemia or hypothermia. The following modes and techniques for surfactant administration are the ones to be used in the present study:

- a. Disconnecting endotracheally intubated neonates from the ventilator, leaving the endotracheal tube

Disconnect the infant momentarily from the ventilator and administer the suspension, as a single bolus, directly into the lower trachea via the endotracheal tube. Perform approximately one minute of hand-bagging and then reconnect the infant to the ventilator at the same settings as before administration.

- b. Without disconnecting endotracheally intubated neonates from the ventilator

Administer the suspension, as a single bolus, directly into the lower trachea by passing a catheter through the suction port into the endotracheal tube or using an endotracheal tube with a side port.

- c. Infants stabilized on nasal continuous positive airway pressure (nCPAP) may also receive surfactant via an endotracheal tube solely introduced for the purpose of surfactant administration or with brief ventilation and rapid extubation. The tube is withdrawn after surfactant administration, and the infant is put on CPAP. If the condition of the baby worsens, standard of care measures could be applied at the discretion of the investigator

The CHF 5633 suspension will be withdrawn from the vial using a sterile syringe through a large-gauge needle (e.g., at least 20 gauge) and the effective dose calculated on the basis of the weight of the neonate could be administered as a single bolus dose or as two half bolus doses into the lower part of the trachea, positioning the neonate on each side as each bolus is being administered.

Since both test treatments will be refrigerated, each vial must be warmed up slowly to room temperature e.g. by placing it in an incubator for about 1 hour or keeping it in hands for 5-10 minutes and gently turned upside down, without shaking, avoiding the formation of foam. Artificial warming methods should not be used.

Re-treatment will be undertaken according to the criteria reported in Section 7.1. The exact time of the rescue treatment will be noted in the appropriate section of the eCRF.

No suctioning of the airways should be performed for two hours after each surfactant instillation unless the treating physician deems this appropriate, in which case this will be noted in the appropriate section of the eCRF.

All used vials will be retained at the site until the conclusion of the trial. Each vial is for single use only. Any leftover medication is to be retained for drug accountability. And any need for re-dosing will require a new vial to be issued via IRT (*see Section 6.6*).

After surfactant administration, the specific method of respiratory support (mechanical ventilation or non-invasive support) will be provided at the discretion of the investigator

